 - r For Subjects on the Q3M (3 monthly) dosing regimen, subjects do not need to attend any visits after Visit 14 (Week 53) where only Vital Signs, Prior/Concomitant Medication, and Adverse Events are scheduled.

Table 15 Dosing Regimen Substudy Schedule of Assessments – (Visits 26 through Follow-Up, Weeks 101 through 157) (revised per Amendment 17)

Phase	Dosing Regimen Substudy																	
Period	Treatment																	
Visit(s) ^a	26	27	28	29	30	31	32	33	34	35	36	37	38	39	40	Early Termination Visit ^b	Follo w-Up	Unscheduled Visit ^c
Substudy Week(s)	101	105	109	113	117	121	125	129	133	137	141	145	149	153	157			
Procedures/Assessments																		
Vital signs ^d	X	X	X	X	X	X	X	X	X	X	X	X	X	X	X	X	X	X
Weight ^e		X				X		X				X			X		X	
Routine physical exam		X						X							X	X	X	X
12-lead ECG ^f		X						X							X	X	X	X
Urine pregnancy test ^g		X				X		X				X			X	X		X
Blood for laboratory tests ^h		X						X							X	X	X	X
Urinalysis		X						X							X	X	X	X
MMSE ⁱ		X						X							X	X	X	X
CDR ⁱ		X						X							X	X	X	X
ADAS-Cog ⁱ		X						X							X	X	X	X
C-SSRS		X						X							X	X	X	X
Safety MRI ^j		X						X							X	X	X	X
Volumetric MRI ^k		X						X							X	X	X	X
Amyloid PET ^l		X													X	X		
Study drug administration Q4w ^m	X	X	X	X	X	X	X	X	X	X	X	X	X	X				
Study drug administration Q3M ^{m,n}			X			X			X			X						
Blood for serum BAN2401 PK ^o			X			X			X			X			X	X	X	X
Blood for exploratory PD biomarker analysis ^p			X			X			X			X			X	X	X	X
Blood for serum anti-BAN2401 ^q			X			X			X			X			X	X	X	X

Prior/concomitant meds	X	X	X	X	X	X	X	X	X	X	X	X	X	X	X	X	X	X	X
Adverse events	X	X	X	X	X	X	X	X	X	X	X	X	X	X	X	X	X	X	X

ADAS-Cog = Alzheimer’s Disease Assessment Scale-Cognitive subscale, C-SSRS = Columbia Suicide Severity Rating Scale, CDR = Clinical Dementia Rating, CDR-SB = Clinical Dementia Rating – Sum of Boxes, ECG = electrocardiogram, IVRS = Interactive Voice Response System, MMSE = Mini-Mental State Examination, MRI = magnetic resonance imaging, OLE = open-label Extension, PET = positron emission tomography, PD = pharmacodynamic, PK = pharmacokinetic, Q3M = every 3 months, Q4W = every 4 weeks, QTcF = corrected QT interval by Fredericia.

- a Assessments should take place on the first day of the study visit in the designated study week except as noted below (footnotes j,k,and l pertaining to imaging assessments). A visit window of ±8 days will be allowed for each visit. If required, and with prior sponsor approval, visits where clinical assessments are conducted may be split such that clinical assessments are performed in order on the 1st day and that the subject and caregiver agree to return to the clinical site on the next consecutive day for study dosing. The remaining assessments can be done on either the 1st or the 2nd day before study drug administration. A visit window of ±7 days will be allowed for the Follow-Up Visit.
- b Subjects who discontinue the Dosing Regimen substudy or discontinue study drug early are requested to undertake the Early Termination Visit (within 7 days after discontinuation the last dose of study drug) and the Follow-Up Visit (3 months after the last dose of study drug). They may also have unscheduled visits for safety assessments.
- c Unscheduled visits may be conducted at any time when safety or MRI data indicates it to be necessary, per protocol or as clinically indicated in the judgment of the investigator. Note that assessments indicated under Unscheduled Visits need not always be conducted – actual assessments needed will be determined by the investigator and will be based on the specific visit needs.
- d Vital signs will be measured both at predose and after infusion. Vital signs should be recorded at least 2 hours after study drug infusion, in addition to predose; however, if at previous Extension Phase visits, no untoward effects of infusion on vital signs are detected ≥2 hours after infusion, these assessments at subsequent study visits may be conducted at a shorter interval after infusion. Vital sign measurements will consist of systolic and diastolic blood pressure (mmHg) measured after at least 3 minutes in a semi supine position, pulse (beats per minute), respiratory rate (per minute), and body temperature (in centigrade)
- e Weight will be taken in the clinic at designated visits. If a subject misses a clinic visit where weight is to be collected, subsequent visits should use the most recent, previous collected weight for infusion calculations until the next clinic visit. Under such circumstances, weight is to be taken at the next clinic visit and entered into the IVRS even if the visit is not designated for weight data collection. If the subject is receiving home infusions, weight measure will be collected one visit before the protocol-specified scheduled weight measurement during the scheduled home infusion. For subjects with weight measurement collected one visit before the protocol-specified schedule, weight measurement will not be needed at the protocol-specified scheduled visit
- f If QTcF is found to be out of range, triplicate ECGs are mandatory.
- g Females of childbearing potential only. For all females of childbearing potential, an additional urine pregnancy test must be done on the day of amyloid PET scanning.
- h Blood for laboratory tests will be taken predose at all visits as indicated.
- i Scales are to be completed in the morning (or, if not possible, consistently at the same time of day) in the following order on the days indicated: MMSE, CDR (including CDR-Global and CDR-SB), and ADAS-Cog. Caregivers/informants (defined as a person able to support the subject for the duration of the study) need only to be present at visits where clinical assessments take place. If required, and with prior sponsor approval, visits where clinical assessments are conducted may be split such that clinical assessments are performed in order on the 1st day and that the subject and caregiver agree to return to the clinical site on the next consecutive day for study dosing. The remaining assessments can be done on either the 1st or the 2nd day.
- j MRI imaging should be conducted at any time following the immediately preceding visit and prior to each of the following Visits for ALL subjects according to the Schedule of Procedures/Assessments. In all cases, the safety MRI must be reviewed by the imaging vendor and a local reader prior to a subject receiving the next dose of study drug. In the event of an Unscheduled Visit, the investigator in consultation with the sponsor will determine whether or not a safety MRI should be conducted. If an Early Termination Visit takes place, an MRI is to be conducted if not already performed during the preceding 90 days.
- k A volumetric MRI sequence will be collected in ALL subjects immediately following all safety MRI assessments.
- l PET in this substudy is optional, but encouraged - A Dosing Regimen substudy baseline amyloid PET assessment should be conducted before substudy Visit 1 (Week 1). Those who are already participating in OLE amyloid PET substudy need not to undertake a baseline PET if they had amyloid PET with in last 3 months as a part of extension phase (at entry).
- m If approved by the Sponsor, and allowable and conducted according to country and local guidelines, subjects may be offered the option of home infusions for approved visits. If a subject begins home infusion during the Dosing Regimen substudy, subjects must be observed for at least 2 hours following the first and second home infusion by the infusion staff. After the third infusion, if no untoward effects of infusion are noted, or infusion reactions can be prevented with prophylaxis, then subjects will be observed 30 minutes after the end of infusion if judged medically stable by the infusion staff.
- n Subjects on the Q3M (3 monthly) dosing regimen do not need to attend any visits after Visit 14 (Week 53) where only Vital Signs, Prior/Concomitant Medication, and Adverse Events are scheduled.
- o If home infusion occurs at visits where PK samples are taken, blood will be taken for the BAN2401 assay only at predose.
- p Blood for serum PD should be taken predose at specified visits.
- q Blood for the BAN2401 anti-drug antibody assay will also be taken at the Early Termination Visit when applicable. At Early Termination and the Follow-Up Visit, the sample can be taken at any time.

STATISTICAL METHODS (revised per Amendments 11, 15, 16, 17, and 19)

Primary Endpoint

- Safety assessments will be based on medical review of AE reports and the results of vital sign measurements, ECG, physical examinations, clinical laboratory tests, anti-drug antibody (ADA) test results, and any relevant test of cognitive function to evaluate decline. Additionally, MRI assessments of microhemorrhage, vasogenic edema, and other clinically significant abnormalities will be evaluated.

Secondary Endpoints

- Change from baselines in brain amyloid levels as measured by amyloid PET at 3 months (Visit 50 [Extension Week 13], Cohort 1) or 6 months (Visit 57 [Extension Week 27], Cohort 2), 12 months and annually thereafter in the Extension Phase (revised per Amendment 15)
- Change from end of Core Study in brain amyloid levels as measured by amyloid PET at the baseline of Extension Phase
- Proportion of amyloid positive subjects over time

Exploratory Endpoints

- Change from baselines in ADCOMS, CDR-SB, ADAS-Cog, and MMSE at each visit assessed
- Time to worsening of CDR global scores, eg, the worsening of global CDR score is defined as an increase from baseline by at least 0.5 points on the global CDR scale on 2 consecutive scheduled visits at which global CDR is measured
- Change from baselines in total hippocampal volume and other biomarkers annually in the Extension Phase (revised per Amendment 15)
- Describe the characteristics, comorbidities, treatments, associated costs for subjects with EAD, and study partner burden up to 5 years before study enrollment, for the duration of the Core Study, the duration of the period between the end of the Core Study and the Extension Baseline (if applicable), the duration of the Extension Phase (if applicable), and for up to 3 years after the end of the Core Study or Extension Phase (where applicable) (revised per Amendment 16)

Dosing Regimen Substudy Endpoints (revised per Amendment 17)

- Change from substudy baseline in brain amyloid levels as measured by amyloid PET
- Change from substudy baseline in plasma A β 42/40 ratio and plasma p-tau181
- Change from substudy baseline in ADCOMS, CDR-SB, ADAS-Cog, and MMSE at each visit assessed
- Safety assessments including, but not limited to, AEs, vital signs, ECG, physical examinations, clinical laboratory tests, anti-drug antibody (ADA). MRI assessments of microhemorrhage, vasogenic edema, and other clinically significant abnormalities
- Population PK parameters of BAN2401 in serum, including but not limited, to AUC, C_{av}, Correlation of PK exposure with biomarkers, safety parameters, and efficacy

ANALYSIS SETS

- The **OLE Full Analysis Set (OLE-FAS)** is the group of subjects who receive at least 1 dose of study drug during the Extension Phase and who have a baseline assessment and at least 1 postdose efficacy measurement during the Extension Phase Part A. The baseline assessment is defined as the last measurement prior to first dose of BAN2401 in the Extension Phase Part A. (revised per Amendments 17 and 19)
- The **OLE Safety Analysis Set** is the group of subjects who receive at least 1 dose of study drug during the Extension Phase Part A. This analysis set is the analysis population used for all safety analyses which will be based on the as-treated principle. (revised per Amendments 17 and 19)
- The **OLE PK Analysis Set** is the group of subjects with at least 1 quantifiable BAN2401 serum concentration with a documented dosing history during the Extension Phase Part A. (revised per Amendment 19)
- The **OLE PD Analysis Set** is the group of subjects who have sufficient PD data to derive at least 1 PD parameter during the Extension Phase Part A. (revised per Amendment 19)

Similar analysis sets will be defined for the Dosing Regimen substudy. The details will be included in the SAP. (revised per Amendment 17)

EFFICACY ANALYSES

An MMRM will be used to analyze the change from baseline secondary efficacy endpoints. Proportion of amyloid positive subjects over time will be summarized.

An MMRM will also be used to analyze the following exploratory endpoints (revised per Amendment 17):

- Change from baseline in the ADCOMS, CDR-SB, ADAS-Cog score, and MMSE score

For each endpoint at a scheduled visit in the Extension Phase, a 90% 1-sided confidence interval will be constructed to test the null hypothesis that the treatment difference between subjects who took placebo in Core Study and those who took 10 mg/kg biweekly in the Core Study is no more than 50% of the treatment difference at the end of Core Study. If the lower limit of this confidence interval is greater than 0, the null hypothesis is rejected. In addition, comparisons between subjects who took placebo at Core Study and those who took 10 mg/kg biweekly in the Core Study will be performed for each endpoint at scheduled visits in the Extension Phase.

Time to worsening of CDR global scores will be analyzed on the FAS using Cox regression model. Time to worsening of CDR global score is defined as time from the first treatment in the Extension Phase to worsening of the CDR score (ie, the first worsening in 2 consecutive scheduled visits). For subjects whose CDR scores have not worsened by the end of study, the time to worsening of the CDR score will be censored at the date of last CDR assessment for these subjects.

Change from baseline in total hippocampal volume and other biomarkers will be summarized using descriptive statistics at scheduled visits in the Extension Phase.

Biomarker and efficacy analysis in the Dosing Regimen substudy will also be performed similarly by dosing regimen. The details will be included in SAP. (revised per Amendment 17)

Additional analyses and summaries will be performed as appropriate.

SAFETY ANALYSES

Safety analysis will be performed similarly to the Core Study. All safety analyses will be based on Safety Analysis Set of the Extension Phase. The incidence of TEAE, laboratory test variables, ECG findings, vital signs, brain MRI, ADAs will be summarized using the descriptive statistics. (See [Section 9.7.1.8](#))

Safety analysis in the Dosing Regimen substudy will also be performed similarly by dosing regimen. The details will be included in SAP. (revised per Amendment 17)

EXPLORATORY ANALYSES

No hypothesis testing will be performed for efficacy variables. Descriptive summary statistics will be generated for the efficacy endpoints as follows:

- Continuous variables will be summarized by number, mean, median, maximum, and minimum
- Categorical variables will be summarized by number and percentage

Additional summary/analyses will be performed using appropriate statistical methodologies if deemed necessary.

SAMPLE SIZE RATIONALE

There is no sample size calculation for the Extension Phase Part A. (revised per Amendment 19)

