27. Planned surgery which requires general, spinal or epidural anesthesia that would take place during the study. Planned surgery which requires only local anesthesia and which can be undertaken as day case without inpatient stay postoperatively need not result in exclusion if in the opinion of the PI this operation does not interfere with study procedures and subject safety.
28. Severe visual or hearing impairment that would prevent the subject from performing psychometric tests accurately

EXTENSION PHASE PART A (revised per Amendments 08, 11, and 19)

29. Subjects who discontinued from the study drug or from the Core Study for reasons other than the following:
 - a. ARIA-E
 - b. ARIA-H (superficial siderosis, macrohemorrhage, or symptomatic microhemorrhage)
 - c. Prohibited or restricted medications that were prohibited during Core Study conduct but are no longer prohibited in the extension phase (revised per Amendment 12)
 - d. Subjects who were APOE4 positive and receiving treatment with BAN2401 10 mg/kg biweekly
 - e. AE that was considered not related to study drug, and that was not severe or life-threatening
30. Females who are breastfeeding or pregnant at Extension Phase Baseline (Extension Screening Visit, as documented by a negative β -hCG assay). A separate baseline assessment is required if a negative screening pregnancy test was obtained more than 72 hours before the first dose of study drug.
31. Females of childbearing potential who:
 - Had unprotected sexual intercourse within 30 days before Extension Phase Baseline and who do not agree to use a highly effective method of contraception (eg, total abstinence, an intrauterine device, a double-barrier method [such as condom plus diaphragm with spermicide], a contraceptive implant, an oral contraceptive, or have a vasectomized partner with confirmed azoospermia) throughout the entire study period and for 28 days after study drug discontinuation.
 - Are currently abstinent, and do not agree to use a double-barrier method (as described above) or refrain from becoming sexually active during the study period or for 28 days after study drug discontinuation.
 - Are who are using hormonal contraceptives but are not on a stable dose of the same hormonal contraceptive product for at least 4 weeks before dosing and who do not agree to use the same contraceptive during the study and for 28 days after study drug discontinuation.

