Any historical amyloid positive PET scan may be used for eligibility upon evaluation by the central imaging CRO. For subjects who wish to participate in the longitudinal imaging substudy, historical amyloid PET scans may not be used as baseline scans for the longitudinal imaging substudy. Required details regarding historical images should be submitted to the CRO medical monitor for evaluation. (revised per Amendment 08)

8. Male or female subjects aged between 50 and 90 years, inclusive
9. MMSE score equal to or greater than 22, and equal to or less than 30 at Screening and Baseline, except for the following countries, where MMSE score must be equal to or greater than 22 and equal to or less than 28 at Screening and Baseline: United Kingdom, Spain, Germany, Sweden, France, and the Netherlands (revised per Amendment 03)
10. Body Mass Index (BMI) >17 and <35 at Screening (revised per Amendment 06)
11. Females must not be lactating or pregnant at Screening or Baseline (as documented by a negative beta-human chorionic gonadotropin assay [β -hCG]). A separate baseline assessment is required if a negative screening pregnancy test was obtained more than 72 hours before the first dose of study drug.
12. All females will be considered to be of childbearing potential unless they are postmenopausal (amenorrheic for at least 12 consecutive months, in the appropriate age group, and without other known or suspected cause) or have been sterilized surgically (ie, bilateral tubal ligation, total hysterectomy, or bilateral oophorectomy, all with surgery at least 1 month before dosing).
13. Females of childbearing potential must not have had unprotected sexual intercourse within 30 days before study entry and must agree to use a highly effective method of contraception (eg, total abstinence, an intrauterine device, a double-barrier method [such as condom plus diaphragm with spermicide], a contraceptive implant, an oral contraceptive, or have a

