vasectomized partner with confirmed azoospermia) throughout the entire study period and for 35 days after study drug discontinuation. If currently abstinent, the subject must agree to use a double-barrier method as described above if she becomes sexually active during the study period or for 35 days after study drug discontinuation. Females who are using hormonal contraceptives must have been on a stable dose of the same hormonal contraceptive product for at least 4 weeks before dosing and must continue to use the same contraceptive during the study and for 35 days after study drug discontinuation.

14. Subjects who are receiving AChEIs or memantine or both for AD must be on a stable dose for at least 12 weeks prior to Baseline. Treatment naïve subjects can be entered into the study. Unless otherwise stated, subjects must have been on stable doses of all other permitted concomitant medications (ie, non-AD related) for at least 4 weeks prior to Baseline. Use of memantine will not be allowed for Japanese subjects (revised per Amendments 01 and 07)
15. Must have an identified caregiver/informant (defined as a person able to support the subject for the duration of the study and who spends at least 8 hours per week with the subject). The caregiver/informant must provide separate written informed consent. In addition, this person must be willing and able to provide follow-up information on the subject throughout the course of the study. This person must, in the opinion of the investigator, spend sufficient time with the subject on a regular basis such that the caregiver/informant can reliably fulfill the study requirements. A permanent caregiver/informant need not be living in the same residence with the subject. For such a caregiver/informant not residing with the subject, the investigator has to be satisfied that the subject can contact the caregiver/informant readily during the times when the caregiver/informant is not with the subject. If in doubt about whether a subject's care arrangements are suitable for inclusion, the investigator should discuss this with the medical monitor. Caregivers/informants need only to be present at visits where clinical assessment of CDR and FAQ takes place. (revised per Amendment 01)

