 - d. Subjects who were APOE4 positive and receiving treatment with BAN2401 10 mg/kg biweekly
 - e. Any reason for discontinuation not related to prohibited medications, including any AE that was considered not related to study drug, and that was not severe or life-threatening
2. Must continue to have an identified caregiver or informant who is willing and able to provide follow-up information on the subject throughout the course of the Extension Phase
 3. Provide written informed consent. If a subject lacks capacity to consent in the investigator's opinion, the subject's assent should be obtained, if required in accordance with local laws, regulations and customs, plus the written informed consent of a legal representative should be obtained (capacity to consent and definition of legal representative should be determined in accordance with applicable local laws and regulations).
 4. Must be able to physically attend clinic visits and be willing and able to comply with all aspects of the protocol

Exclusion:

1. Subjects who discontinued from the study drug or from the Core Study for reasons other than the following:
 - a. ARIA-E
 - b. ARIA-H (superficial siderosis, macrohemorrhage, or symptomatic microhemorrhage)
 - c. Prohibited or restricted medications that were prohibited during Core Study conduct but are no longer prohibited in the Extension Phase
 - d. Subjects who were APOE4 positive and receiving treatment with BAN2401 10 mg/kg biweekly
 - e. AE that was considered not related to study drug, and that was not severe or life-threatening
2. Females who are breastfeeding or pregnant at Extension Phase Baseline (Extension Screening Visit, as documented by a positive β -hCG assay). A separate baseline assessment is required if a negative screening pregnancy test was obtained more than 72 hours before the first dose of study drug.
3. Females of childbearing potential who:
 - Had unprotected sexual intercourse within 30 days before Extension Phase Baseline and who do not agree to use a highly effective method of contraception (eg, total abstinence, an intrauterine device, a double-barrier method [such as condom plus diaphragm with spermicide], a contraceptive implant, an oral contraceptive, or have a vasectomized partner with confirmed azoospermia) throughout the entire study period and for 28 days after study drug discontinuation.

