- Are currently abstinent, and do not agree to use a double-barrier method (as described above) or refrain from becoming sexually active during the study period or for 28 days after study drug discontinuation.
- Are who are using hormonal contraceptives but are not on a stable dose of the same hormonal contraceptive product for at least 4 weeks before dosing and who do not agree to use the same contraceptive during the study and for 28 days after study drug discontinuation.

(NOTE: All females will be considered to be of childbearing potential unless they are postmenopausal [amenorrheic for at least 12 consecutive months, in the appropriate age group, and without other known or suspected cause] or have been sterilized surgically [ie, bilateral tubal ligation, total hysterectomy, or bilateral oophorectomy, all with surgery at least 1 month before dosing]).

4. Subjects who develop the following conditions from the time of completion of the Core Study to the start of the Extension Phase:
 - a. Contraindications to MRI scanning, including cardiac pacemaker/defibrillator, ferromagnetic metal implants (eg, in skull and cardiac devices other than those approved as safe for use in MRI scanners)
 - b. Other significant pathological findings on brain MRI at Extension Phase Baseline (Extension Screening Visit), including but not limited to: any macro-hemorrhage (greater than 10 mm at greatest diameter), which is currently symptomatic or worsened since the Core Study; any area of superficial siderosis, which is currently symptomatic or worsened since the Core Study; evidence of vasogenic edema, which is severe or symptomatic; aneurysms, vascular malformations, infective lesions, evidence of multiple lacunar infarcts or stroke involving a major vascular territory, severe small vessel, or white matter disease or space occupying lesions or brain tumors (however lesions diagnosed as meningiomas or arachnoid cysts and <1cm at their greatest diameter need not be exclusionary)
 - c. Any immunological disease which is not adequately controlled, or which requires treatment with biologic drugs during the study
 - d. Bleeding disorder that is not under adequate control (including a platelet count <50,000 or INR >1.5)
 - e. Receiving treatment with anticoagulant therapy but anticoagulation control is not optimized and is stable for at least 4 weeks before Extension Phase Baseline (Extension Screening Visit)

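### The Extension contraception exclusion joins its paired conditions with *and* instead of *or*, so it misses some women who refuse contraception on study

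*Protocol*

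**What the plan says.** **Core rule.** Section 9.3.1, inclusion 13 (same text in the synopsis) says that a woman who could become pregnant "must not have had unprotected sexual intercourse within 30 days before study entry and must agree to use a highly effective method of contraception". Users of hormonal contraceptives must have been on a stable dose "for at least 4 weeks before dosing and must continue to use the same contraceptive during the study".

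**Extension rule.** Appendix 4, exclusion 3, excludes females of childbearing potential who fall under any of three bullets:

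- Bullet 1: "Had unprotected sexual intercourse within 30 days before Extension Phase Baseline and who do not agree to use a highly effective method of contraception".
- Bullet 2: "Are currently abstinent, and do not agree to use a double-barrier method (as described above) or refrain from becoming sexually active".
- Bullet 3, for hormonal users who "are not on a stable dose of the same hormonal contraceptive product for at least 4 weeks before dosing and who do not agree" to stay on the same contraceptive.

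Synopsis exclusion 31 has the same three bullets; its third reads in part "for at least 4 weeks before dosing and who do not agree to use the same contraceptive during the study".

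**Pregnancy criterion.** Synopsis exclusion 30 excludes pregnant women "as documented by a negative β -hCG assay". Appendix 4 exclusion 2 has "as documented by a positive β -hCG assay".

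**The concern.** Two requirements that must both be met become, when stated as an exclusion, two failures either of which excludes. The joining word has to change from *and* to *or*. In bullets 1 and 3 it did not change, so the Extension excludes only women who fail both parts of a pair.

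As a result, the criterion admits a woman of childbearing potential who declines contraception during open-label treatment, which is the case it exists to prevent. No other Extension eligibility text requires contraception. Inclusion 4 asks for willingness to comply with the protocol, but the only Extension contraception rule to comply with is this exclusion.

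**Working it through.** There is no plan figure to reproduce; the check is one of logic.

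**Bullet 1, sexually active woman on a non-hormonal method** (bullets 2 and 3 cannot apply). Let A = unprotected intercourse within 30 days and B = refuses contraception on study.

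| A | B | Core inclusion 13 | Extension exclusion 3 |
|---|---|---|---|
| no | no | admits | does not exclude |
| yes | no | bars | does not exclude |
| no | yes | bars | does not exclude |
| yes | yes | bars | excludes |

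Core bars A *or* B, which is 3 of 4. The Extension excludes A *and* B, which is 1 of 4. The two middle rows differ.

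**Bullet 3, hormonal user with no recent unprotected intercourse.** Let A = dose not stable and B = will not keep the same contraceptive. The pattern is the same: Core bars 3 of 4, the Extension excludes 1 of 4, and the two women who fail only one half differ.

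**Bullet 2** is sound. Being abstinent is a condition for the bullet to apply and is not itself a failure, so *and* is correct there.

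**All profiles together.** Cross contraceptive status with recent unprotected intercourse, agreement to contraception and, for hormonal users only, dose stability. Abstinent women are taken to have had no recent unprotected intercourse.

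| Status | Profiles | Fail Core 13 | Excluded by Extension | Escape |
|---|---|---|---|---|
| Non-hormonal | 2 × 2 = 4 | 3 | 1 | 3 − 1 = 2 |
| Hormonal | 2 × 2 × 2 = 8 | 7 | 3 | 7 − 3 = 4 |
| Abstinent | 2 | 1 | 1 | 1 − 1 = 0 |
| Total | 14 | 11 | 5 | 11 − 5 = 6 |

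The six that escape are:

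1. Non-hormonal, no recent unprotected intercourse, refuses.
2. Non-hormonal, recent unprotected intercourse, agrees.
3. Hormonal, stable dose, no recent unprotected intercourse, refuses.
4. Hormonal, unstable dose, no recent unprotected intercourse, agrees.
5. Hormonal, stable dose, recent unprotected intercourse, agrees.
6. Hormonal, unstable dose, recent unprotected intercourse, agrees.

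Profile 1 is the decisive one. Bullet 1 fails because there was no unprotected intercourse, bullet 2 because she is not abstinent, and bullet 3 because she uses no hormonal method.

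**After the change.** With *or* in bullets 1 and 3, the Extension excludes 3 + 7 + 1 = 11 profiles, the same 11 that fail Core 13. It does not catch abstinent women by accident, because total abstinence is itself on the list of highly effective methods in bullet 1.

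**The case against.** The case against rests mainly on impact, and most of it stands.

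- **Few women are affected.** Core entry age was 50 to 90, and the Extension follows later, so few subjects are of childbearing potential.
- **Entry to Part A is effectively closed.** Under Amendment 19 ongoing Part A subjects move to Part B, whose only criterion is current Part A enrolment. A rewording now would change almost no enrolment decision.
- **There are other protections.** A serum pregnancy test is done at Extension screening and urine tests during treatment, and a subject who becomes pregnant must be withdrawn. The Core agreement covers the whole study period and arguably carries over. Even so, tests detect a pregnancy and do not prevent one, and the Extension sets its own post-treatment window of 28 days against 35 in the Core, which weakens the carry-over reading.
- **The Extension rule may be deliberately looser.** Amendment 12 says it meant to widen Extension entry. Admitting a woman who had unprotected intercourse, tests negative and agrees to contraception could be intended. So could admitting a hormonal user with a recent dose change who will continue, and a stable user who gives up one product may simply switch to another effective method. These are fair points about profiles 2 to 6. They cannot explain profile 1, and the amendment's rationale does not mention contraception.
- **The wording can be read differently.** Bullets 1 and 3 repeat *who* after *and*, which could be taken as naming a second excluded group. This is the less natural reading, although a site that knows the Core rule might well apply the evident intent.

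The counts above are of logical cells, not of women, and say nothing about frequency.

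**Conclusion.** The concern holds. Read literally, Appendix 4 exclusion 3 and synopsis exclusion 31 are weaker than Core inclusion 13 in bullets 1 and 3, and 6 of the 14 profiles pass that the Core rule would bar. The clear gap is the sexually active woman on a non-hormonal method who refuses contraception on study; the other five matter only if the Extension was meant to mirror the Core rule, which the parallel structure suggests but no text states.

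The importance is low. The affected group is very small, entry to Part A is effectively closed, and no analysis or data are touched. The error is nonetheless in an operative eligibility rule that gives the wrong answer if followed. The wrong assay result in synopsis exclusion 30 is purely clerical and adds no weight.

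**What to change.** In Appendix 4 exclusion 3 and synopsis exclusion 31, replace *and* with *or* before *who do not agree* in bullets 1 and 3. Leave bullet 2 unchanged. In synopsis exclusion 30, change *negative* to *positive* to match Appendix 4 exclusion 2.

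The cost is 2 bullets × 2 places = 4 one-word edits, plus one in synopsis exclusion 30, 5 in all. No procedure, schedule or data item changes. It does not justify an amendment of its own and can go into the next one made for other reasons.
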